**A nomogram model to predict central lymph node metastasis in
thyroid papillary carcinoma suitable for primary hospitals**

Date updated: December 6, 2021

Study Protocol and Statistical Analysis Plan

Collection of Patients

1000 Patients who underwent total thyroidectomy or lobectomy and were diagnosed as PTC by pathological examination between June 2014 and September 2019 in Sun Yat-sen Memorial Hospital (Guangzhou, South China) and 200 patients in the First Affiliated Hospital of Zhengzhou University (Zhengzhou, North China) from March 2019 to November 2020 were selected as the subjects to construct the nomogram. The inclusion criteria were as follow: (1) underwent TC operation for the first time; (2) confirmed as PTC by postoperative pathological examination; (3) underwent ipsilateral or bilateral CLND. The exclusion criteria included: (1) complicated with other subtypes of TC or thyroid metastatic cancer; (2) received preoperative interventional therapy (such as radiofrequency and microwave therapy) or head and neck radiotherapy. the patient recruitment process was showed in Figure1. We randomized them at 7:3 and divided it into a training set and a verification set. Besides, 200 cases that met the inclusion and exclusion criteria above-mentioned in the First affiliated Hospital of Zhengzhou University were enrolled as a external verification set.

[figure not shown]

Fig 1. the recruitment process of patients in our study

Surgical Quality Control

All surgeries were conducted by at least two experienced surgeons. According to the preoperative US, all patients in our study underwent total thyroidectomy or lobectomy plus ipsilateral or bilateral CLND and then all specimens were for paraffin fixation and histological analysis in the department of pathology.

Baseline Characteristics

The following clinical features for each patient were obtained before surgery: gender, age, occupation, complicated with autoimmune diseases (absent / present), history of radiation exposure (absent / present), family history of thyroid cancer (absent / present), with other tumors (absent / present) and preoperative laboratory examinations including neutrophil count, lymphocyte count, platelet count, thyroid-stimulating hormone (TSH), free triiodothyronine (fT3), free thyroxine (fT4), anti-thyroglobulin antibody (TgAb), thyroid peroxidase antibody (TPOAb).

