Preoperative US signatures of thyroid tumors were also included: distribution (unilateral / bilateral), shape (regular / irregular), maximum diameter, number (single / multiple), boundary (clear / semiclear / unclear), component (solid /cystic-solid), calcification (absent / microcalcification / macrocalcification), blood flow (absent / internal / annular), cervical lymph node enlargement (absent / present).

Statistical Analysis

Statistical analyses were performed using the Statistical Package for the Social Sciences (SPSS) for Windows, Version 25.0 and RStudio software. All tests were two-tailed, and a two-sided value of $P<0.05$ was considered statistically significant. The continuous variables for normally distributed data are presented as the mean \pm standard deviation (SD) and were compared by using the Student's t-test. For the variables with a skewed distribution, data are presented as medians (interquartile ranges). The categorical variables are reported as frequencies (percentages), and the characteristics of the patients were compared by using the chi-square test. A least absolute shrinkage and selection operator (LASSO) regression analysis conducted by using the glmnet R package was applied to identify the important preoperative predictors associated with CLNM in the training set, with the optimal values of the penalty parameter λ determined via 10-fold cross-validation. Multivariate logistic regression analysis were conducted to determine the potential nonlinear association between predictors and the risk of CLNM. Odd ratios (ORs), 95% confidence interval (CI) and probability values were obtained by logistic regression analysis. The area under the receiver operating characteristic (ROC) curve (AUC) was calculated to evaluate the accuracy of the nomogram for predicting CLNM. The calibration curve and Hosmer-Lemeshow tests were performed to evaluate the calibration of the nomogram. The decision curve analysis (DCA) was applied to validate clinical utility of the nomogram.

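### Calibration is to be judged by a curve and a Hosmer-Lemeshow test alone; adding the calibration intercept and slope with 95% CIs in the verification sets would say how large the misfit is and how uncertain

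*Combined protocol and SAP*

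**What the plan says.** The Statistical Analysis section deals with calibration in one sentence: "The calibration curve and Hosmer-Lemeshow tests were performed to evaluate the calibration of the nomogram". It does not name the patient set, the number of groups or the degrees of freedom.

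The only confidence intervals in the plan belong to the odds ratios: "Odd ratios (ORs), 95% confidence interval (CI) and probability values were obtained by logistic regression analysis". The one numerical decision rule covers every test, and so Hosmer-Lemeshow too: "All tests were two-tailed, and a two-sided value of $P<0.05$ was considered statistically significant".

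Under Collection of Patients, the Guangzhou cohort has 1000 patients, and the plan says "We randomized them at 7:3 and divided it into a training set and a verification set". The Zhengzhou set is described as follows: "200 cases that met the inclusion and exclusion criteria above-mentioned in the First affiliated Hospital of Zhengzhou University were enrolled as a external verification set".

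**The concern.** A nomogram hands each patient a predicted risk, and the title says this one is meant for primary hospitals. A reader there needs to know how far that risk may be off in new patients. The planned decision curve analysis also works on absolute risks, so it depends on calibration.

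The curve gives a picture without a stated uncertainty. The test gives a p-value, which mixes the amount of misfit with the size of the set. Neither yields an estimate with an interval. If moderate misfit usually leaves the test non-significant at these set sizes, the plan's only numerical result on calibration will often look reassuring when the risks are off by several points.

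The choice of set matters too. If the nomogram is an unpenalised logistic model, its calibration intercept is 0 and its slope 1 in the training data by construction. Only the verification sets can then show a shift or overfitting.

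**Working it through.** The plan states no power or precision figure for calibration, so there is none to reproduce.

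**Inputs from the documents.** External set: 200. Internal verification set: 0.3 × 1000 = 300 if the 7:3 split covers the Guangzhou patients, or 0.3 × 1200 = 360 if it covers all patients. Significance level: 5%, two-sided.

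**Assumptions, not in the documents.** The linear predictor is normal with mean -0.3 or -1 and SD 0.75, 1 or 1.3. This gives mean risk 29-44% and AUC about 0.69-0.79. The test uses 10 equal groups. Ranges below are the minimum and maximum over these six distributions, by simulation.

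**Step 1: the test.** HL = Σ (O − E)² / [E(1 − E/m)], where O and E are the observed and expected events in a group of m patients. No parameter is estimated from the verification data, so the reference is chi-square with 10 df. Under perfect calibration it rejects in 4.0-5.5% of runs. With 8 df it rejects in about 10-12%.

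**Step 2: a uniform shift.** True logit = predicted logit ± 0.3. For example, mean predicted risk is 44% and the truth is 38% or 50%, a difference of 6 points.

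| Method | n = 200 | n = 300 |
|---|---|---|
| Hosmer-Lemeshow, 10 df | 9-27% | 15-38% |
| Direct test of the intercept | 39-51% | 53-70% |

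The second row can be checked by hand. With the linear predictor as offset, the expected 95% half-width of the intercept is 0.297-0.340 at n = 200, so SE = 0.297/1.96 = 0.152 to 0.340/1.96 = 0.173. Power ≈ Φ(0.3/SE − 1.96), which is Φ(0.02) = 51% to Φ(−0.23) = 41%. At n = 300 the half-width is 0.242-0.277, so SE = 0.123-0.141 and power is about 68% to 56%. Both agree with the simulation.

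**Step 3: overfitting.** The true AUC is held at 0.69-0.79 and the predicted logits are stretched by 1/slope, with and without recentring.

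| Calibration slope | Detected by Hosmer-Lemeshow (10 df) |
|---|---|
| 0.8 | 11-29% at n = 200; 14-37% at n = 300 |
| 0.7 | 24-62% at n = 200 |
| 0.5 | 86-99% at n = 200 |

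If the spread of the predictions is held fixed instead, the true AUC at slope 0.8 falls to 0.66-0.75 and power is 10-25% and 11-31%. The conclusion for moderate misfit is the same. At slope 0.5 that construction lowers the true AUC to 0.60-0.67 and gives 43-93% at n = 200.

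**Step 4: the other reading of the split.** At n = 360, with assumed prevalence 30-50% and AUC 0.70-0.79, a 0.3 shift is detected in 22-43% and a slope of 0.8 in 18-32%.

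**Step 5: precision of the proposed measures.** Expected 95% half-widths under good calibration:

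| Measure | n = 200 | n = 300 |
|---|---|---|
| Slope | ±0.33-0.48 | ±0.27-0.39 |
| Intercept | ±0.30-0.34 | ±0.24-0.28 |

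In a central case (prevalence 40%, AUC 0.74), a Wald test finds a slope of 0.8 in 26% at n = 200 and 37% at n = 300. Hosmer-Lemeshow finds it in 17% and 21%.

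**The case against.** The strongest reply is that the plan pairs the test with a calibration curve, and an attentive reader of the curve will see direction and rough size. This stands: it would be wrong to infer that nothing planned shows how large the misfit is. What is missing is a numerical estimate with its uncertainty.

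A reader might also infer that a non-significant test will be declared good calibration. The plan does not say so. It does offer no other numerical criterion, so that reading is left open.

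Nor is the test uninformative. It detects gross overfitting well, and a shift of 0.5 logit in about half or more of studies in the central case (52-61% at n = 200, 77-80% at n = 300).

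The slope remedy is modest. With an interval of about ±0.33-0.48 at n = 200, 0.8 often cannot be separated from 1. This also stands. The interval makes the imprecision visible but does not remove it.

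Finally, someone might go on to fault the 7:3 split. The documents give no ground for that here: a random held-out set is a valid check of overfitting, and this point does not depend on changing it.

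**Conclusion.** The point holds as a gap in what will be reported; no planned result becomes invalid. At the sizes of the verification sets, a Hosmer-Lemeshow p-value above 0.05 is weak evidence against moderate miscalibration. In the external 200, a shift of about 6 percentage points in mean risk would be missed in about 73-91% of studies (100 minus 9-27), and a slope of 0.8 in about 71-89% (100 minus 11-29).

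The percentages rest on assumed risk, AUC and predictor spread, on 10 groups with 10 df, and on the test being run in verification data. The size of 300 is one reading of the split. With 360 the figures improve somewhat, but moderate misfit is still missed more often than found. That the plan contains no calibration estimate with an interval rests on its text alone.

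**What to change.** In the external 200 and in the internal verification set, report beside the planned curve:

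- the calibration intercept, from a logistic model with the nomogram's linear predictor as offset, with a 95% CI;
- the calibration slope, from a logistic model on that linear predictor, with a 95% CI.

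Make Hosmer-Lemeshow secondary. Run it on the verification data, state the grouping, and set the df equal to the number of groups. State that a non-significant result will not be interpreted as good calibration.

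The cost is a few lines in the SAP and two simple logistic fits per set, with no new patients, no refit of the nomogram and no change to the split. The downside is wide intervals, above all for the slope in the external set. The main gain is for a uniform shift, where the direct intercept test has 39-51% power at n = 200 against 9-27% for Hosmer-Lemeshow.

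### As specified, the decision curve analysis can show that the nomogram beats treat-all and treat-none, but not that it adds to the ultrasound node finding

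*Combined protocol and SAP*

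**What the plan says.** The Statistical Analysis section closes with the only text on clinical utility: "The decision curve analysis (DCA) was applied to validate clinical utility of the nomogram". It gives no reference strategy, threshold range, measure of uncertainty or criterion for calling the nomogram useful. The only 95% confidence interval in the plan belongs to the logistic odds ratios.

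The Collection of Patients section defines three data sets. The main cohort is "1000 Patients who underwent total thyroidectomy or lobectomy". On the split it says "We randomized them at 7:3 and divided it into a training set and a verification set". The external set is "200 cases that met the inclusion and exclusion criteria above-mentioned". The decision curve is assigned to none of the three.

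The ultrasound node finding is recorded as one of the candidate predictors: "cervical lymph node enlargement (absent / present". The Surgical Quality Control section adds "According to the preoperative US, all patients in our study underwent total thyroidectomy or lobectomy plus ipsilateral or bilateral CLND".

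**The concern.** A decision curve is normally drawn against two defaults: treat everyone and treat no one. Any model that contains one informative predictor will beat both over some range of thresholds. If the ultrasound node finding is informative, a nomogram that merely repackages it can be presented as clinically useful, whatever the other candidates contribute.

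The title aims the nomogram at primary hospitals. A user there who already has the ultrasound report wants to know whether a multi-item score improves on it. The data to answer that are in hand, but the plan does not ask the question. Because no data set is named, it also allows the curve to be drawn in the data used to select and fit the model, where it flatters the model.

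**Working it through.** **Inputs from the documents.** A main cohort of 1000 split 7:3 gives 700 training and 300 internal verification patients; the external set has 200. (If the split covered all 1200, it would be 840/360; the simulations use 700/300.) There are 24 candidate variables: 7 demographic or history items, 8 laboratory values and 9 ultrasound items. Selection is by LASSO, "with the optimal values of the penalty parameter λ determined via 10-fold cross-validation", without saying whether the minimum or the one-standard-error penalty is meant.

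**Inputs not in the documents, assumed.** Prevalence of central node metastasis (CLNM) 0.30, 0.40 and 0.50; several sensitivity/specificity pairs for the node sign; and the rule for reading the curve. The plan states no net-benefit figure, so there is none to reproduce.

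**Step 1: why the defaults are easy to beat.** Net benefit at threshold t is NB(t) = TP/n − (FP/n) × t/(1−t). At t = prevalence p:

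- treat-none: 0
- treat-all: p − (1−p) × p/(1−p) = 0
- acting on a binary sign: p × sens − (1−p)(1−spec) × p/(1−p) = p × (sens + spec − 1)

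The last line is positive for any sign better than chance. With sensitivity 40%, specificity 85% and p = 0.40, it is 0.40 × 0.25 = 0.10.

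**Step 2: over what range.** The sign beats both defaults for t between 1−NPV and PPV. In the same example PPV = 0.16/(0.16 + 0.09) = 0.64 and 1−NPV = 0.24/(0.24 + 0.51) = 0.32. That width of 0.32 is less than half of the 0.80-wide range 0.10-0.90, so a strict reading of the curve gives a very different answer from a lenient one.

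**Step 3: simulation when the nomogram truly adds nothing.** Training n = 700, verification n = 300 or 200. The node sign is the only possible signal, beside 26 noise columns. Models: full logistic, node-only, and LASSO followed by logistic with either penalty. There were 300 runs per setting for the full and node-only models. For LASSO there were 100 runs, at prevalence 0.40 and n = 300 only, with signs 50/50, 20/90, 30/90 and 50/80. Monte Carlo standard error is at most about 3 and 5 points respectively.

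| Node sign (sens/spec) | Reading of the curve against the two defaults | Looks useful |
|---|---|---|
| 30/90 to 60/80 | above both at some threshold | 99-100% |
| 30/90 to 60/80 | above both at t = prevalence | 73-100% |
| 30/90 to 60/80 | above both over more than half of 0.10-0.90 | 0-79% |
| 30/90 to 60/80 | never below either over 0.10-0.90 | 0-35% |
| 20/90 | above both at some threshold | 95-99% (full or node-only), 93% (LASSO minimum), 48% (LASSO one-SE) |
| 50/50 (uninformative) | above both at some threshold | 89-93% (full), 23-31% (node-only), 42% (LASSO minimum), 10% (LASSO one-SE) |

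**Step 4: with a node-only comparator.** The paired bootstrap 95% interval for the net-benefit difference at t = prevalence excluded zero in the nomogram's favour in about 0-1% of runs for an informative sign (30/90 to 60/80), 0-2% at 20/90 and 1-5% at 50/50. On the point estimate alone, the nomogram still looked better than node-only in about 0-21% of runs with an informative sign. The interval therefore matters as well as the comparator.

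**Step 5: why held-out data.** A separate simulation used 24 candidates, LASSO at the minimum penalty and thresholds of 1-99%. With no informative predictor at all, the lenient reading endorsed the model in 62-68% of training sets, and in every training set where LASSO kept a predictor. With a 40/85 node sign as the only signal, the nomogram-versus-node interval, averaged over an illustrative 20-60% range, favoured the nomogram in 25-30% of training sets but in at most 0.5% of verification sets.

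**Step 6: precision when there is real added value.** In one simulation, four informative predictors of 0.5 SD each gave a lower limit above zero in 73-91% of 200-patient sets and 89-97% of 300-patient sets. At 0.35 SD the figures were 42-57% and 59-74%. In another, a true rise in AUC from about 0.63 to 0.72 was detected in only 42-45% of 200-patient sets.

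**The case against.** The strongest reply is that beating treat-all and treat-none is a legitimate question and that decision curve analysis answers it correctly. Every patient had central node dissection, so treat-all is the practice observed and a relevant comparator. A model containing a truly informative node sign really does have net benefit over the defaults near t = prevalence, so its endorsement is not an error. This stands. The limitation is that the result says nothing about added value over ultrasound.

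A reader might infer that the planned analysis would declare the nomogram useful about 100% of the time, or almost regardless of the data. The documents do not support that. They state no rule for reading the curve, no node-sign accuracy and no prevalence, and the rate moves from 99-100% to 0-35% as these change. In the Step 5 simulation with no informative predictor, the lenient reading endorsed the model in only about half of verification sets (47-51%).

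A reader might also infer that the node sign decided who had dissection. The Surgical Quality Control section says only that surgery followed preoperative ultrasound. Nobody went without dissection, and the recorded sign is cervical, not specifically central. Node-only is a sensible added comparator, not a decision rule that the documents establish.

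Finally, the plan also has odds ratios with intervals, AUC and calibration. If the node sign is retained, the odds ratios bear on whether other predictors add to it. They do not measure net benefit.

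**Conclusion.** The omission is real: comparator, data set, threshold range and interval are all unstated, and against the two defaults alone the analysis cannot establish added value over the ultrasound node finding. Step 1 shows this algebraically for any sign better than chance.

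The frequencies are conditional. They are rates given that the nomogram adds nothing, and they rest on assumed accuracy, prevalence and reading of the curve. Nothing in the documents shows that this nomogram adds nothing; as written, the decision curve would not reveal it either way. Under the lenient reading the rate is about 99-100% for signs of 30/90 to 60/80 and 48-99% at 20/90; stricter readings bring it down to 0-79% or 0-35%.

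This is a cheap improvement to the plan, not a flaw that invalidates the study.

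**What to change.** Replace the decision curve sentence with a specification along these lines:

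- Run the analysis with the frozen nomogram in the internal and external verification sets. Any training-set curve is descriptive only.
- Compare with treat-all, treat-none and a model containing ultrasound cervical node enlargement alone, fitted in the training set.
- Have the investigators fix the threshold range before the curves are drawn.
- Report the net-benefit difference, nomogram minus node-only, with a bootstrap 95% confidence interval.
- Limit any statement of added utility over ultrasound to what that interval supports. Do not make it a pass/fail gate in the 200-patient external set, because Step 6 shows that such a gate would often miss real gains.

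The cost is SAP wording and a few lines of R. No new data are needed, since the node finding is already among the planned variables. The downside is that the interval may be wide at n = 200, so a modest gain may have to be reported as not shown.
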